9.6 Safety Oversight (ISM plus SMC)

9.6.1 Independent Safety Monitor (ISM)

The ISM is a physician with relevant expertise whose primary responsibility is to provide independent safety monitoring in a timely fashion. The ISM will review SAEs in real time and other AEs as needed and provide an independent medical assessment and recommendation to DMID. The participating VTEU site will have an ISM with experience in infectious diseases or internal medicine, in close proximity to the participating VTEU site, and have the authority to readily access study participant records.

9.6.2 Safety Monitoring Committee (SMC)

Safety oversight will be conducted by a SMC that is an independent group of experts that monitors subject safety and advises DMID. The SMC members will be separate and independent of study personnel participating in this study and should not have scientific, financial or other conflict of interest related to this study. The SMC will consist of members with appropriate expertise to contribute to the interpretation of the data from this study.

The SMC will review study progress and participant, clinical, safety, and reactogenicity data at the following time points:

- Organizational meeting: Prior to start of the study
- Data Review Meeting (DRM): After 15-day reactogenicity data are available for the first 25 subjects
- Ad hoc meetings: When a halting rule is met, for immediate concerns regarding observations during this study, or as needed.

Final review meeting: Approximately 6 months after final clinical database lock to review the cumulative unblinded safety data for this trial. The data will be provided in a standard summary format. The SMC may be asked to provide recommendations in response to questions posed by DMID. The SMC will operate under the rules of a DMID-approved charter that will be approved at the organizational meeting of the SMC. At this time, each data element that the SMC needs to assess will be clearly defined. Procedures for SMC reviews/meetings will be defined in the charter. The SMC will review applicable data to include, but not limited to, study progress and

participant, clinical, safety, and reactogenicity data. Reports may include enrollment and demographic information, medical history, concomitant medications, physical assessments, and solicited and unsolicited AE/SAEs. Additional data may be requested by the SMC, and interim statistical reports may be generated as deemed necessary and appropriate by DMID. The SMC may receive data in aggregate and presented by treatment arm. The SMC may also be provided with expected and observed rates of the expected AEs in an unblinded fashion, and may request the treatment assignment be unblinded for an individual subject if required for safety assessment.

The SMC will review grouped and unblinded data in the closed session only. The SMC will meet and review this data at scheduled time points or ad hoc as needed during this study as defined in the SMC charter. As an outcome of each review/meeting, the SMC will make a recommendation as to the advisability of proceeding with study vaccinations (as applicable), and to continue, modify, or terminate this study.

DMID or the SMC chair may convene the SMC on an ad hoc basis according to protocol criteria or if there are immediate concerns regarding observations during the course of the study. The DMID Medical Monitor is empowered to stop enrollment and study vaccinations if adverse events that meet the halting criteria are reported. The DMID Medical Monitor and the ISM will be responsible for reviewing SAEs in real time. The SMC will review SAEs on a regular basis and ad hoc during the study.

10 CLINICAL MONITORING

10.1 Site Monitoring Plan

Site monitoring will be conducted to ensure that human subjects protections, study and laboratory procedures, study intervention administration, and data collection processes are of high quality and meet sponsor, ICH/GCP guidelines and applicable regulations, and that this study is conducted in accordance with the protocol, protocol-specific MOP and applicable sponsor standard operating procedures. DMID, the sponsoring agency, or its designee will conduct site-monitoring visits as detailed in the clinical monitoring plan. Site visits will be made at standard intervals as defined by DMID and may be made more frequently as directed by DMID. Monitoring visits will include, but are not limited to, review of regulatory files, accountability records, eCRFs, informed consent forms, medical and laboratory reports, and protocol compliance. Site monitors will have reasonable access to the participating VTEU site, study personnel, and all study documentation according to the DMID-approved site monitoring plan. Study monitors will meet with the site principal investigators to discuss any problems and actions to be taken and document visit findings and discussions.

11 STATISTICAL CONSIDERATIONS

The goals of this study are to assess the immunologic response, safety, and tolerability of lyophilized BPZE1 administered intranasally at 10^7 CFU compared to 10^9 CFU, in healthy volunteers 18-49 years of age. Subjects in three of four treatment arms (45 of 50 expected subjects) will be vaccinated using the VaxINator device. In addition, the study will enroll a small number of subjects (5 expected) who will receive lyophilized BPZE1 administered by needleless tuberculin syringe to allow for historical, informal comparisons to previous Phase 1 data. This study is designed as a randomized, placebo controlled, partially-blind (i.e., the method of immunization [VaxINator vs. needleless syringe] will be known) clinical trial evaluating the safety and immunogenicity of a single dose of either 10^7 CFU or 10^9 CFU of BPZE1 delivered by intranasal VaxINator device or needleless tuberculin syringe.

11.1 Study Hypotheses

This Phase 2a study is not designed to test a formal null hypothesis. Rather, it is intended to obtain preliminary estimates of the safety and immune response induced by the BPZE1 lyophilized vaccine in healthy adults. See [Section 3](#) for Study Objectives and Outcome Measures.

11.2 Sample Size Considerations

The study population for this clinical trial includes healthy male and non-pregnant female subjects 18-49 years of age, inclusive, who meet all eligibility criteria. Study subjects will be recruited from the general population at the Vanderbilt University Medical Center VTEU site. This study is planned to enroll approximately 50 healthy adults randomized into four treatment groups in a 3:3:3:1 ratio, as described in [Table 2 \(Section 4\)](#). The tables below describe the probability of observing safety events and the minimum detectable difference in seroconversion rates for the planned sample size.

[Table 3](#) indicates the probability of observing one or more safety events (such as solicited local or systemic reactogenicity events, or an unsolicited non-serious AE of a particular type) for a treatment arm with the assumed event frequency and for the given sample size. For example, for any of the treatment arms with a sample size of 15 subjects, there is a 79.4% probability of detecting an AE that occurs at a frequency of 10%, and a 14% probability if the AE occurs at a rate of 1%.

Table 3: Probability (%) of Observing at Least One Adverse Event

| Event Frequency | N = 5 | N=15 |
|------------------------|--------------|-------------|
| ≥0.01% Rare | <0.1 | <0.1 |
| ≥0.1% Uncommon | 0.5 | 1.5 |
| ≥1% Common | 4.9 | 14.0 |
| ≥10% Very Common | 41.0 | 79.4 |

One of the secondary outcome measures is the proportion of subjects that achieve seroconversion to individual pertussis antigens (PT, FHA, PRN, and FIM 2/3) by serum IgG or IgA ELISA at Days 15, 29 and 181 for humoral immune response. Table 4 shows the minimum detectable differences with 80% power between the proportion of subjects attaining seroconversion in the BPZE1 by VaxINator group versus Placebo using a two-sided Fisher’s Exact test and alpha = 0.05.

Table 4: Minimum Detectable Difference in Proportion of Subjects Attaining Seroconversion comparing Placebo versus the BPZE1 (107 or 109 CFU)

| Placebo by VaxINator | BPZE1 (10 ⁷ or 10 ⁹ CFU) by VaxINator | Assumed Proportion of Subjects Attaining Seroconversion (Placebo) | Proportion of Subjects Attaining Seroconversion (BPZE1) | Minimum Detectable Difference (Treatment – Placebo) |
|----------------------|---|---|---|---|
| N=15 | N=15 | 0.00 | 0.41 | 0.41 |
| | | 0.01 | 0.43 | 0.42 |
| | | 0.05 | 0.54 | 0.49 |
| | | 0.10 | 0.63 | 0.53 |
| | | 0.20 | 0.76 | 0.56 |

N=Sample Size

11.3 Planned Interim Analyses

Interim analyses would only be used to terminate this trial in the event that unanticipated safety events deemed to be of sufficient concern require such action by the sponsor. These interim assessments will not be made based on testing a formal statistical hypothesis; therefore, p-value adjustment will not be made to any analyses.

11.3.1 Interim Safety Review

An ISM and SMC will be convened by DMID to review study progress and participant, clinical, safety, and reactogenicity data, as described in [Section 9.6](#). An interim safety review may include enrollment and demographic information, medical history, concomitant medications, physical assessments, clinical laboratory values, dosing compliance, solicited and unsolicited AE/SAEs, and *B. pertussis* colonization data. Additional data may be requested by the SMC, and interim statistical reports may be generated as deemed necessary and appropriate by DMID. The SMC may receive data in aggregate and presented by treatment arm, including expected and observed rates of the expected AEs. The SMC will review grouped data in the closed session only. The SMC will meet and review this data at scheduled time points or ad hoc as needed during this trial as defined in the SMC charter. As an outcome of each review/meeting, the SMC will make a recommendation as to the advisability of proceeding with study vaccinations (as applicable), and to continue, modify, or terminate this trial.

Additionally, this trial will be monitored to determine if any of the halting rules described in [Section 9.5](#) are met.

A preliminary report prepared with data through Day 46 (or Day 29 if no subjects remain colonized with *B. pertussis* at the Day 29 visit) will be prepared as described in [Section 11.4](#). This report will include analyses of safety data.

11.3.2 Interim Immunogenicity Review

A preliminary report of safety and immunogenicity and *B. pertussis* colonization data through Day 46 (or Day 29 if no subjects remain colonized with *B. pertussis* at the Day 29 visit) will be prepared. The analyses presented in this report will be released while subjects remain in the trial for long-term safety and immunogenicity follow-up, and will be included in the final analysis of these data.

11.4 Final Analysis Plan

The results obtained from this study will be used to inform the dose recommended for a subsequent Phase 2b study. Clinical, safety, reactogenicity, immunogenicity and *B. pertussis* colonization data through approximately 45 days after study vaccination, or 28 days after study vaccination if no subjects remain colonized with *B. pertussis* at Day 29, will represent the primary clinical database for this trial. Once the last subject completes the visit that occurs approximately 45 days after study vaccination (or approximately 28 days after study vaccination, if no subjects remain colonized with *B. pertussis* at the Day 29 visit), the primary clinical database will be cleaned, monitored, and frozen. Analyses of safety, reactogenicity, immunogenicity, and *B. pertussis* colonization data by treatment arm are planned, including descriptive summaries of 15-day reactogenicity data, 28-day adverse event data (including SAE, NOCMC and AESI), 28 and 45-day nasal clearance data, and humoral and mucosal immunogenicity data through Day 46 (or Day 29 if no subjects remain colonized with *B. pertussis* at the Day 29 visit). As it is anticipated that subjects will remain in long term immunogenicity and safety follow-up at the time of these analyses, the presentation of these data will not include any unblinded listings of individual subject data and aggregate summaries will be in a format that prevents inadvertent unblinding of the sponsor or clinical investigators to any individual subject's treatment assignment or immune response data.

A preliminary report will be prepared by the DCC after the primary clinical database is cleaned, monitored, and frozen and all immunogenicity and colonization data through Day 46 (or Day 29 if no subjects remain colonized with *B. pertussis* at the Day 29 visit) are received. These analyses may be made available to DMID and the vaccine company partner and to the lead principal investigator for planning subsequent trials. These analyses will not be used to make any decisions concerning the conduct of this trial. A formal statistical analysis plan that defines the analyses of data to be included in the preliminary report for early release and the CSR will be developed and finalized prior to the to the Day 46 data freeze (or Day 29 if no subjects remain colonized with *B. pertussis* at the Day 29 visit).

Analysis of Day 181 humoral and mucosal immunogenicity data may be performed and released as the data are available from the research laboratories. Any such analyses would be considered the final analysis for the endpoint, and included in the CSR.

Once the last subject completes the last visit, the final clinical database will be cleaned, monitored and locked. Unblinded analyses of safety, reactogenicity, colonization, and available immunogenicity data will then be performed by the DCC and will be included in the CSR. All safety analyses will be performed using the safety population, all immunogenicity analyses will be performed using the immunogenicity and the per-protocol (PP) populations, whereas all

colonization data will be summarized using per-protocol population. The analysis populations are defined below ([Section 11.4.1.](#))

All analyses will be presented by treatment group (i.e. group by BPZE1 10^9 CFU, BPZE1 10^7 CFU, or Placebo). In addition, results for BPZE1 at dose of 10^9 CFU will be further grouped by vaccination device (group by VaxINator or needleless tuberculin syringe) to allow for comparison of immunogenicity results with previous results from Phase 1 clinical trials of BPZE1 (these previous trials used needleless tuberculin syringe as device for administration).

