4 STUDY DESIGN

This is a phase 2a, single center, randomized, partially blind, placebo controlled, clinical trial evaluating a single intranasal dose of either 10^7 CFU or 10^9 CFU of BPZE1 in healthy adults (18-49 years of age, inclusive). The study will evaluate a lyophilized formulation of the product, with the goal of testing for the optimal dose for subsequent clinical trials. Since it is anticipated that the VaxINator device will be the primary mechanism of delivery in subsequent clinical trials, the majority of volunteers will receive vaccine or placebo via VaxINator device. Five individuals will receive 10^9 CFU of BPZE1 by needleless tuberculin syringe in order to compare immunogenicity to previous Phase 1 clinical trials of BPZE1.

We anticipate that enrollment will require approximately 12 months, with each subject participating for 6 months. Fifty healthy adults, 18-49 years of age will be randomized to one of four treatment groups in a 3:3:3:1 ratio, as described in the table below. Safety will be assessed through an Independent Safety Monitor (ISM) and a Safety Monitoring Committee (SMC) described in [Section 9.6](#).

Table 2: Treatment Groups and Intranasal Vaccine to be Administered

| Group | N | Intranasal Vaccination | Device Used for Administration |
|-------|----|------------------------|--------------------------------|
| 1 | 15 | BPZE1 10^7 CFU | VaxINator |
| 2 | 15 | BPZE1 10^9 CFU | VaxINator |
| 3 | 15 | Placebo | VaxINator |
| 4 | 5 | BPZE1 10^9 CFU | Needleless Tuberculin Syringe |

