8.1. Secondary Immunogenicity Analysis

Summaries and analysis of immunogenicity data will be presented for the immunogenicity and PP populations by treatment group.

Immune responses in terms of toxin-specific serum IgG and IgA antibody titers (PT, FHA, PRN, FIM 2/3) will be summarized at each time point. Analyses will include the Geometric Mean Titers (GMTs) along with corresponding 95% confidence intervals (Table 17, Table 18, Table 19, and Table 20) and Geometric Mean Fold Rise (GMFR) (Table 21, Table 22, Table 23, and Table 24), as well as the proportion of subjects achieving seroconversion (defined as 2-fold increase over baseline of GMT) for each antigen (PT, FHA, PRN, and FIM 2/3) and the proportion of subjects that achieved seroconversion for ≥ 1 (Table 25 and Table 26) and ≥ 2 (Table 27 and Table 28) antigens (PT, FHA, PRN, and FIM 2/3.) Rates of seroconversion will be compared using Barnard's exact test. Reverse cumulative distributions (RCD) curves will also be presented for PT, FHA, PRN, and FIM 2/3 antibody titers. Plots for each assay will be generated with four panels (pre-vaccination, Day 15, Day 29, and Day 181), and separate curves within each panel for each treatment group, as shown in Figure 3, Figure 4, Figure 5, and Figure 6. Individual immunogenicity response data will also be presented (Listing 7 and Listing 8.)

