9.3.1. Solicited Events and Symptoms

Systemic and mucosal (local) solicited adverse events will be collected from the time of study vaccination through 14 days after study vaccination. Systemic events include: fever, chills, fatigue, malaise, myalgia, arthralgia, headache, and hypersensitivity. Mucosal events include: runny nose, stuffy nose/congestion, nasal pain/irritation, epistaxis, sneezing, sinus pressure/pain, sore throat, cough, and shortness of breath. Solicited AEs will be summarized by severity for each day after the study vaccination (Days 1-14 post study vaccination) and as the maximum severity over all 15 days ([Table 38](#), [Table 40](#), [Table 41](#), [Table 42](#), [Table 43](#), [Table 44](#), [Table 45](#), [Table 46](#), [Table 47](#), [Table 48](#), [Table 49](#), [Figure 9](#), [Figure 10](#), [Figure 11](#), and [Figure 12](#).) Severity will be graded on a scale of 0 (absent), 1 (mild), 2 (moderate) and 3 (severe). Grading scales for mucosal and systemic solicited adverse events are presented in [Table 6](#), [Table 7](#), and [Table 8](#), respectively. Additionally, solicited AEs will be analyzed by taking the most severe response over the follow-up period, dichotomizing into a binary variable (none versus mild, moderate, or severe) and using standard techniques, such as exact confidence intervals, to summarize the proportion of subjects reporting each symptom, any local symptom, and any systemic symptom ([Table 39](#).) Summaries of solicited AEs will be presented by treatment arm ([Table 36](#).) The proportion of subjects reporting symptoms will be compared between treatment arms using Chi-square or Fisher's exact test ([Table 37](#).) Solicited adverse events by subject will be presented in [Listing 10](#) and [Listing 11](#).

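### Dose choice is a stated use of the results, but no 10^9-versus-10^7 difference, ratio or confidence interval is pre-specified

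*Protocol*

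**What the plan says.** **Purpose.** Protocol section 4 describes the trial as run "with the goal of testing for the optimal dose for subsequent clinical trials". Section 11 gives the goal as assessing "lyophilized BPZE1 administered intranasally at 10^7 CFU compared to 10^9 CFU, in healthy volunteers". Section 11.4 adds: "The results obtained from this study will be used to inform the dose recommended for a subsequent Phase 2b study". Section 11.1 qualifies this: "This Phase 2a study is not designed to test a formal null hypothesis"; the aim is preliminary estimates.

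**Design.** "Fifty healthy adults, 18-49 years of age will be randomized to one of four treatment groups in a 3:3:3:1 ratio", that is 15 (10^7 VaxINator), 15 (10^9 VaxINator), 15 (placebo VaxINator) and 5 (10^9 syringe).

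**Planned contrasts.**
- Protocol 11.2 and Table 4 give "minimum detectable differences with 80% power between the proportion of subjects attaining seroconversion in the BPZE1 by VaxINator group versus Placebo".
- SAP 8.1: "Rates of seroconversion will be compared using Barnard's exact test". No pair is named. In Tables 21-32 the difference, its 95% CI and the p-value are filled only for the two VaxINator dose columns, and the footnote names placebo as the reference.
- SAP 9.3.1: "The proportion of subjects reporting symptoms will be compared between treatment arms using Chi-square or Fisher's exact test". Again no pair is named. Table 37 shows a difference and CI against placebo only.
- Tables 17-20 (GMT) and Table 33 (colonization) give per-arm estimates with CIs and no contrast.

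**Arm definition.** Protocol 11.4 groups results by dose first and then splits 10^9 by device. The SAP columns (section 6.1) are always split by device, with no pooled 10^9 column.

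**The concern.** A choice between two doses rests on the difference between them and on how well that difference is known. The plan supplies neither figure. Two dose-versus-placebo results do not replace it: if both doses clearly beat placebo, those contrasts say little about how the doses differ from each other.

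The SAP preface says that the document describes all planned analyses. A dose contrast computed later would therefore be unplanned. Someone would have to decide, with results in view, which CI method to use, which endpoints and days matter, and whether 10^9 means 15 subjects or 20. In a pooled arm of 20 the five syringe subjects carry a quarter of the weight (5/20), so each of them moves the 10^9 rate by 5 points.

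**Working it through.** **1. Reproduce the plan's own figure (Table 4).** Inputs from protocol 11.2: n = 15 v 15, two-sided Fisher exact test, alpha 0.05, 80% power. Power = sum over all 16 x 16 outcomes of Bin(a; 15, p1) x Bin(b; 15, p2), counting outcomes with p <= 0.05.

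| Placebo | BPZE1 (Table 4) | Power at that rate | Rate solved for 80% |
|---|---|---|---|
| 0.00 | 0.41 | 80.5% | 0.408 |
| 0.01 | 0.43 | 79.2% | 0.434 |
| 0.05 | 0.54 | 80.5% | 0.537 |
| 0.10 | 0.63 | 79.3% | 0.635 |
| 0.20 | 0.76 | 80.5% | 0.758 |

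Table 4 reproduces. It concerns dose against placebo only.

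**2. Precision of the missing contrast.** Both VaxINator dose arms have n = 15. Newcombe interval for d = p9 - p7, with Wilson limits (l, u) for each arm:

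lower = d - sqrt[(p9 - l9)^2 + (u7 - p7)^2]; upper = d + sqrt[(u9 - p9)^2 + (p7 - l7)^2].

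Example, 15/15 v 14/15. Wilson limits are 0.796 to 1.000 and 0.702 to 0.988; d = 0.067.
- Lower: 0.067 - sqrt(0.204^2 + 0.055^2) = -0.144.
- Upper: 0.067 + sqrt(0 + 0.232^2) = 0.298.

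| 10^9 v 10^7 (illustrative counts) | Difference | 95% CI | Width |
|---|---|---|---|
| 15/15 v 15/15 | 0.00 | -0.20 to 0.20 | 0.41 |
| 15/15 v 14/15 | +0.07 | -0.14 to 0.30 | 0.44 |
| 14/15 v 12/15 | +0.13 | -0.13 to 0.39 | 0.52 |
| 13/15 v 10/15 | +0.20 | -0.11 to 0.47 | 0.57 |
| 8/15 v 8/15 | 0.00 | -0.32 to 0.32 | 0.64 |

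Widths run from about 40 to 65 points.

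**3. Difference needed for 80% power.** Suppose every 10^9 subject responds, and X of 15 respond at 10^7. Fisher rejects when X <= 10 (15/15 v 10/15: p = 0.042). Barnard rejects when X <= 11 (15/15 v 11/15: p = 0.043). Power is then P(X <= 10) or P(X <= 11) for X ~ Bin(15, p7).
- 80% power, Fisher: p7 = 0.592, a difference of 0.41. This is row 1 of Table 4 with responders and non-responders swapped (1 - 0.41 = 0.59).
- 80% power, Barnard: p7 = 0.662, a difference of 0.34.
- Illustration with the Phase 1b rates in protocol 2.1.2 (0.92 v 1.00): power 0.5% (Fisher) or 2.7% (Barnard). Those rates came from the liquid formulation and also required a level at least four times the detection limit. This trial counts any two-fold rise, so they are a guide only.

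**4. GMT ratio.** The documents give no SD, so log10 SD is assumed. The 95% CI is the ratio times or divided by 10^(2.048 x SD x sqrt(2/15)), with t on 28 df. For SD 0.3, 0.4, 0.5 and 0.6 the factor is 1.68, 1.99, 2.37 and 2.81.

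**5. Number of added cells.** Tables 21-24: 4 antigens x 4 time points x 4 tables = 64. Tables 25-28: 4 x 4 = 16. Tables 29-30: 4 x 3 x 2 = 24. Tables 31-32: 2 x 2 = 4. Table 33: 2. Total 110. GMT ratios in Tables 17-20 at two days add 4 x 2 x 4 = 32. Table 37 adds about 20 symptom lines.

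**The case against.** **This is a descriptive phase 2a trial.** No listed objective in protocol section 3.1 compares the doses, section 2.1 gives the primary purpose as evaluating the lyophilized formulation, and results are to inform a later dose rather than settle it. All true. It rules out asking for a powered dose test, and none is asked for here. An interval without a p-value fits the estimation aim, arguably better than the Barnard p-values already in the shells.

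**The estimates are there.** A reader might infer that the trial will yield no estimate of the dose difference. The documents do not support that. Each dose has its own column with n, estimate and 95% CI, and reverse cumulative curves and individual listings are planned. The difference follows by subtraction, and an interval for proportions follows from the counts. What remains is that neither the method nor the 10^9 arm is fixed in advance. The preliminary report for those planning later trials also omits the listings.

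**The text names no pair.** SAP 8.1 and 9.3.1 would allow a dose contrast, and protocol 11.4.2 leaves the pair open for solicited events. This stands as to the text. The shells that carry the comparisons specify placebo.

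**Selection by p-value.** A reader might also infer that the dose will be picked because one dose reaches p < 0.05 against placebo and the other does not. No such rule is written, and SAP 8.1 says that no formal hypothesis testing is planned. The layout permits that misreading: with placebo at 1/15, 6/15 gives Barnard p = 0.043 and 5/15 gives p = 0.100, though the doses differ by one subject (+6.7 points, 95% CI -25 to +37). It remains a possible misuse, not a planned one.

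**Conclusion.** The point holds as a gap in pre-specification. Comparing 10^7 with 10^9 is a stated goal and informing the next dose is a stated use, but no dose-to-dose difference, ratio or CI is planned for any endpoint. At 15 per arm the interval for a proportion would span about 40 to 65 points. With 10^9 at 100%, 80% power needs a difference of about 34 points (Barnard) or 41 points (Fisher).

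These figures assume that all 15 subjects in each VaxINator arm contribute a result; losses would widen the intervals. The counts in the table are illustrative, and the GMT factors rest on an assumed SD.

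No planned result becomes invalid and no data are lost. Severity: should-fix.

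**What to change.** 1. In SAP 8.1 and 9.3.1, name the contrast: 10^9 VaxINator minus 10^7 VaxINator, descriptive, 95% CI, no p-value. State the CI method and say that the syringe arm is not pooled into it.
2. Add that row to Tables 21-32, 33 and 37.
3. In Tables 17-20 add the 10^9/10^7 GMT ratio with 95% CI, with Days 29 and 181 as the key time points. The shells hold Day 181 back from the preliminary report, so only Day 29 would appear there.
4. In SAP section 5 add that with 15 per arm the 95% CI for a dose difference in a proportion spans about 40 to 65 points, and that 80% power needs about 34 points (Barnard, 100% v 66%) or 41 points (Fisher, 100% v 59%).

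**Cost.** No new data or visits. The tables grow by about 110 immunogenicity and colonization cells, plus the GMT ratios and the solicited-symptom lines, all unadjusted for multiplicity. Naming key time points limits selective reading, but only for the GMT ratios. The dose comparison will look visibly imprecise.
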